
C.3. Study II – Intervention Trial (Aim 2)

C.3.1. Design Overview

ASSESS																					
	IG + G	G	G	G	a	G	a	G	a	G	a	a	G	a	a	G	a	a	G		
eTARGET	IT + T	Т	Т	Т	t	Т	t	Т	t	Т	t	t	Т	t	t	Т	t	t	Т		
Month	0	1	2	3	4	5	6	7	8	9	10	11	12	13	14	15	16	17	18	21	24
Assessment	В			AF			FF			AF			FF			AF			FF	AF	FF
logond																					

Table 3: Overview of Study Design: Interventions and Assessments

Legend

ASSESS = Assessment Only; GENERIC = Generic Self-Help; eTARGET = Targeted E-Cigarette Self-Help; Assessments = Assessment Points; IG = Generic Stop Smoking for Good initial brochure; IT = Targeted If You Vape initial brochure; G = Generic Stop Smoking for Good booklet; T = Targeted If You Vape booklet; g = Generic supportive letter and tri-fold pamphlet; t = Targeted supportive letter and tri-fold pamphlet; B = Baseline Assessment;

AF = Abbreviated Follow-up assessments; FF = Full Follow-up assessments. Shading indicates the duration of the intervention.

We propose a three-arm randomized design (N = 2900) with the following conditions: (1) Assessment Only (ASSESS; n = 580), the no-treatment control; (2) Generic Self-Help (GENERIC; n = 1160), which will Research Strategy Page 9

include the Enhanced (non-targeted) cessation booklets from our cessation study and 9 intermittent (nontargeted) motivational pamphlets (C.1.2.3.), and (3) targeted e-cigarette booklets (eTARGET; n = 1160), which will be the full intervention developed in Study I, expected to comprise an initial brochure, a series of 10 If You Vape booklets and 9 intermittent motivational pamphlets delivered over 18 months. Importantly, GENERIC and eTARGET will be exactly matched in amount of contact and content. Assessments will occur at 3-month intervals, over 24 months. An overview of the design is depicted in Table 3.

Specific Aim 2 (the RCT) will be tested with a comparison of smoking-cessation outcomes of eTARGET vs both ASSESS and GENERIC conditions. A secondary outcome will be cessation of e-cigarettes themselves. The comparison of GENERIC versus ASSESS will address whether an untargeted intervention is sufficient for dual users. A secondary outcome will be cessation of e-cigarettes themselves. Additionally, the cost-effectiveness of both active interventions will be calculated in reference to ASSESS, as per Specific Aim 3. Secondary analyses will involve surveillance of both tobacco and e-cigarette use over time.

C.3.2. Participants

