We believe that it is feasible to accrue the target N of 2900 during the 18 months we have allocated for accrual. In the previous self-help cessation study (C.1.2.3), we successfully recruited 1874 smokers over 16 months. Although the current study will be limited to smokers using e-cigarettes (dual users), which is a smaller population base, it is nevertheless substantial and growing. Because all contact with participants will be by telephone, internet, and mail, we are not geographically limited. The rate of accrual is limited only by the amount of advertising, staffing levels, and logistic requirements of screening callers and processing baseline data. The tremendous response to our survey (C.1.4) indicates that we can efficiently reach large numbers of potential participants. We have a history of meeting our accrual goals, even with notoriously difficult populations that required adjustments to accrual strategies. Most notably, we have recruited participants from a much smaller segment of the population: 700 women in months 4-8 of their pregnancy who had already quit smoking and were interested in relapse-prevention assistance (Brandon et al., 2012; Lopez et al., 2008).

C.3.3. Study Arms

In this section, we describe the rationale and form of the three intervention conditions. Note that participants in both the GENERIC and eTARGET conditions will have the option of receiving electronic versions of the intervention materials via a link to a website (see C.7.2).

C.3.3.1. Assessment Only (ASSESS). Participants in this condition will not receive any intervention materials. They will participate solely in the repeated assessments. Including this comparison condition controls for the effect of repeated assessments and allows for the most meaningful evaluation of the efficacy effect size as well as the cost-effectiveness of the eTARGET intervention. This condition will also be the primary source of data for the secondary surveillance aim regarding naturalistic changes in smoking and ecigarette use over time.

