C.4.1.3. Follow-Up Assessments. Participants will be sent follow-up assessments (by mail or email link) at 3-month intervals through 24 months, as indicated in Table 3. The length of the follow-up (24 months post-enrollment) was calculated by adding the standard 6 months after the end of the eTARGET intervention. We deliberately keep each follow-up assessment brief to minimize participant burden and consequent attrition. Each of these follow-ups will include an assessment of the use of tobacco products, e-cigarettes, pharmacotherapies, and other tobacco cessation aides or services since the previous contact. These data will constitute the Abbreviated Follow-Ups, and will be sufficient for calculating treatment outcomes as well as for the longitudinal tracking of cigarette and e-cigarette usage for the secondary aim. Full Follow-Ups at 6, 12, 18, and 24 months will include most of the questionnaires from the baseline assessment, as well as additional domains, including evaluation of the intervention (Client Satisfaction Questionnaire; Attkisson & Greenfield, 1994), self-reported use of the material (i.e., how much they read, how often they refer back, how much it affected their behavior), current intentions to guit smoking and to guit e- cigarettes, and the three motivationrelated scales administered at baseline. The 24 month follow-up will also include an 12-item measure of health outcomes (SF-12[™] Health Survey; Ware, J E, Kosinski, M, Keller, S D., 1995), 2001). Research staff will attempt to contact participants to complete any missing data on the completed baseline and follow-up assessments.

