At each assessment point we will calculate point-prevalence abstinence rates (for tobacco smoking as well as e-cigarette use) using 7-day, 30-day, and 90-day criteria. Point-prevalence measures are best for capturing the dynamic nature of cessation, maintenance, and relapse. The 7-day criterion will serve as our primary outcome index. Continuous abstinence is not feasible because guit dates will be highly variable across participants, and also because one goal of the intervention is to encourage lapsers to guit again (recycle). We need our outcome measures to reflect these changes in smoking status over time. However, the 30-day and 90-day point-prevalence abstinence criteria also reflect more prolonged abstinence than the 7day criterion usually used in treatment studies (Velicer et al., 1992). We will also compare groups on continuous measures, such as current smoking rate (cigarettes/day), months of smoking during the follow-up period, length of current abstinence period, and latency from quit date to relapse. Outcomes will be reported that account for missing follow-up data using both multiple imputation (MI) and intent-to-treat (ITT) approaches.

C.5. Cost-Effectiveness Analysis (Aim 3)

The relative effectiveness and costs of the intervention compared to standard care will be measured based on the health care system perspective. Using the trial endpoint results, effectiveness will be predicted in terms of smoking cessation and translated into life years and quality adjusted life years (QALY) based on published associations between smoking cessation and long-term health outcomes (Cohen & Fowler, 1993; Torrance, 1986). Costs include the intervention costs, collected prospectively, and lifetime costs of reduced medical expenditures attributable to smoking cessation, that will be modeled using published estimates (e.g., Berman et al., 2013; Cowan & Schwab, 2011; Fishman et al., 2003; Hockenberry et al., 2012; Hodgson, 1992; Oster et al., 1984). No out-of-pocket costs or transfer payments (i.e., increased social security due to longevity) will be incorporated into the analysis, because they do not fall within the system perspective. In addition, costs associated only with research (e.g., mailing of assessments) will be excluded. Monetary values will be inflation adjusted, and all outcomes will be presented in discounted and undiscounted values.

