The effectiveness and cost results will also be presented as incremental cost-effectiveness ratios, specifically cost per quitter, cost per life year, and QALY. We will assess the robustness of incremental results between the three study arms using probabilistic sensitivity analysis. In our previous study of Forever Free as a relapse-prevention intervention, we found that the cost per non-relapse at 24 months was \$186, and the cost per extra QALY was \$83 at a 4% discount rate (Brandon et al., 2004). In addition, the parallel incremental costs of supplementing an existing smoking cessation intervention with the Forever Free booklets were estimated at \$4,225 and \$2,385, respectively (Chirikos et al., 2004). Both estimates are well below the \$50,000 per QALY typically applied in health policy recommendations, and they compare very favorably to counseling, pharmacotherapy, and telephone quitline interventions (Cromwell et al., 1997; Hollis et al., 2007). These results may refine public health decisions between alternative modalities.

C.6. Data Management and Analysis

C.6.1. Data Management

Data will be input through screens created by the Data Systems Team within Moffitt's Research Computing Support Group (Research IT) and will be subject to computerized range and consistency checks. The data will then populate an Access database, which will also be created and maintained by Research IT. This process will be supervised jointly by the PI and Study Data Manager/Staff Biostatistician. The database will be converted on a monthly basis to a SAS database (SAS Institute, Cary, NC). This database and SAS will be used by the statistician who will provide the PI with reports and summaries on a regular basis and perform the final analyses. To ensure participant confidentiality, unique identifiers will be expunged from this data set. **C.6.2. Sample Size and Study Power Analysis**

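### The health-system cost-effectiveness analysis (C.5) costs no concomitant cessation treatment, so cost per quitter is biased if system-paid use differs by arm

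*Combined protocol and SAP*

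**What the plan says.** **Perspective and costs (C.5).** "The relative effectiveness and costs of the intervention compared to standard care will be measured based on the health care system perspective". On cost components: "Costs include the intervention costs, collected prospectively, and lifetime costs of reduced medical expenditures attributable to smoking cessation". C.5 then lists what it leaves out: out-of-pocket costs and transfer payments, because they lie outside the system perspective, and costs that arise only from the research.

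**Concomitant treatment.** C.3.2 does not exclude people who use quitlines, websites or pharmacotherapy. It records that use so that its impact can be examined statistically. Only current enrolment in a face-to-face programme bars entry. C.4.1.2 asks about pharmacotherapy and other aids at baseline, and C.4.1.3 includes in each 3-monthly follow-up an "assessment of the use of tobacco products, e-cigarettes, pharmacotherapies, and other tobacco cessation aides or services since the previous contact". No section gives this use a unit cost or adds it to an arm's total.

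**Comparators.** C.3.1 states that "the cost-effectiveness of both active interventions will be calculated in reference to ASSESS, as per Specific Aim 3". In C.3.3.1, the entry for ASSESS reads "Participants in this condition will not receive any intervention materials", and including this arm "allows for the most meaningful evaluation of the efficacy effect size as well as the cost-effectiveness of the eTARGET intervention". C.3.3.2 sets GENERIC against both ASSESS and eTARGET on cost-effectiveness. C.5 adds: "We will assess the robustness of incremental results between the three study arms using probabilistic sensitivity analysis".

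**The concern.** C.5 excludes out-of-pocket spending because the health system does not bear it. By the same test, cessation treatment that the system does pay for belongs in the total. It appears neither among the listed costs nor among the listed exclusions.

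The two sides of the ratio are then treated differently. A quit that a prescription or a quitline helped to produce enters the effect, while the resource that helped produce it enters no cost. Booklets may prompt people to seek such help, or may replace it. In the first case the booklets look cheaper per quitter than they are, and in the second dearer. Section C.6.4.2 names pharmacotherapy use as an example of a group difference that may need adjustment in the efficacy model. The plan therefore foresees arm differences in use for the effect but not for the cost.

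This matters more than usual because the intervention is cheap, so a small uncosted difference can be large beside the cost of the booklets. Cost-effectiveness is also one of the trial's primary aims.

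**Working it through.** The plan states no cost per quitter for this trial, so there is no figure to reproduce.

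**Inputs from the protocol**
- Planned abstinence (C.6.2): at most 15% in ASSESS by 18 months, with increments of at least 5 points. I take 15%, 20% and 25%. The effect difference dE is 0.10 for eTARGET versus ASSESS, and 0.05 for GENERIC versus ASSESS and for eTARGET versus GENERIC.
- Earlier relapse-prevention results (C.5): $186 per non-relapse and $83 per QALY; for adding booklets to an existing programme, $4,225 and $2,385. The threshold cited is $50,000 per QALY.
- Effect in the earlier trial (C.1.2.2): 22% versus 32% relapsed.

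**Assumed, because the documents give nothing:** a between-arm difference in use of 1 to 10 points, and a system cost of $100 to $400 per user.

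**Step 1. Size of the error.** Let dC be the incremental cost per participant that C.5 counts, and dK the omitted between-arm difference in system-paid treatment cost per participant.

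Reported ratio = dC / dE. Full ratio = (dC + dK) / dE. Error = dK / dE.

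For dK = $1 the error is 1 / 0.10 = $10, or 1 / 0.05 = $20. For dK = 0 it is zero.

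**Step 2. Range, with dK = difference in use x cost per user**

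| Difference in use | Cost per user | dK | Shift, 10-point effect | Shift, 5-point effect |
|---|---|---|---|---|
| 1 point | $100 | $1 | $10 | $20 |
| 5 points | $100 | $5 | $50 | $100 |
| 5 points | $200 | $10 | $100 | $200 |
| 10 points | $200 | $20 | $200 | $400 |
| 10 points | $400 | $40 | $400 | $800 |

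Each shift can be positive or negative.

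**Step 3. Scale against booklet cost.** Suppose the earlier $186 is incremental and belongs with that trial's 10-point effect. The implied cost is 186 x 0.10 = $18.60 per participant. Carried over to this trial:
- eTARGET versus ASSESS: 18.60 / 0.10 = $186. With dK = +$10 it becomes 28.60 / 0.10 = $286; with dK = -$10, 8.60 / 0.10 = $86.
- GENERIC versus ASSESS: 18.60 / 0.05 = $372. With dK = +$10 it becomes $572; with dK = -$10, $172.
- Even dK = $5 moves $186 by $50, which is 50 / 186 = 27%.

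For eTARGET versus GENERIC, both arms receive a brochure, 10 booklets and 9 pamphlets. Their delivery costs should largely cancel, so dK could form much of the increment. The $18.60 figure does not apply to that contrast.

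**Step 4. Scale against the decision threshold.** The earlier results imply 186 / 83 = 2.24 and 4,225 / 2,385 = 1.77 QALYs per non-relapse. If a quitter gains about as much (an assumption), the largest shift in the table, $800, is 800 / 2.24 = $357 to 800 / 1.77 = $452 per QALY. That is 0.7% to 0.9% of $50,000.

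**The case against.** **The cost list may not be exhaustive.** The verb is include, so other system costs could be added at analysis. That is a fair reading. But C.5 also lists its exclusions, and this item is on neither list, so the choice is left until results are known. The modelled lifetime expenditures do not fill the gap: they are published estimates tied to quitting and cannot reflect differences in treatment use between these arms.

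**Much of the use may be self-paid or free.** This stands. Self-paid aids are openly and consistently excluded, and only the system-paid share matters. The documents describe no item on payer or quantity.

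**Use may not differ by arm.** This also stands, above all for GENERIC and eTARGET, which are matched in contact. The bias would then be zero.

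**No decision changes.** On the assumptions above, the shift is below 1% of the cited threshold. This stands for cost per QALY. It does not answer the point for cost per quitter, which C.5 also reports.

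Two stronger readings are tempting. A reader might infer from the words standard care that the comparator is undefined, or that ASSESS is presented as usual care. The documents do not support this: C.3.1 and C.3.3.1 give ASSESS the reference role, and it is described throughout as receiving no treatment. The phrase is a wording conflict and makes no ratio wrong. A reader might also infer from C.3.1 that eTARGET versus GENERIC is only available indirectly. C.3.3.2 plans that comparison on cost-effectiveness, and C.5 covers increments between all three arms.

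**Conclusion.** The point holds as a conditional one. Under its own perspective, C.5 should either count system-paid cessation treatment or say that it is left out; it does neither. Cost per quitter shifts by $10 or $20 for each $1 per participant of omitted between-arm difference, at effects of 10 and 5 points. The sign is unknown, and the shift is zero if system-paid use is equal across arms.

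It would go too far to say that the planned cost per quitter is wrong. That would need evidence that use differs, and the documents have none. The dollar ranges rest on assumed use and unit costs, and the comparison with booklet cost rests on carrying over the earlier trial's $186. No change of conclusion against $50,000 per QALY is shown, and the efficacy analysis is untouched. This is a cheap improvement to a primary aim.

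**What to change.** In C.5:
1. Add to each arm's costs the cessation services and pharmacotherapy reported at the 3-monthly follow-ups, valued at published unit costs.
2. State a range for the system-paid share and for the quantity used, and vary both in the probabilistic sensitivity analysis already planned.
3. Report this ratio beside the one that counts booklet costs only.
4. Replace standard care with the arm names, so that C.5 agrees with C.3.1, C.3.3.1 and C.3.3.2.

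The cost is some extra analysis; use is already asked about, so participants carry no new burden. The downside is that unit costs and the payer split must be assumed, because the documents describe no item that supplies them, and cost per quitter may look less favourable.

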Specific Aim 1. To create a minimal smoking-cessation intervention for current dual users of tobacco cigarettes and e-cigarettes (Study I). The intervention will comprise a series of booklets modeled after the *Forever Free* booklets found to be successful at producing long-term abstinence among the general population of smokers, but adapted to the special needs, circumstances, and risk factors of dual users. Validated methodologies used for adapting the intervention mirror those used in our prior smoking cessation studies, and reflect systematic approaches across three-phases informed by focus group and learner verification methodologies. The intervention will provide assistance for smoking cessation, and also encourage users to taper and eventually terminate their e-cigarette use as per traditional NRT. The end product of Study I will be a series of booklets tentatively titled, *"If You Vape: Guide to Quitting Smoking,"* available both in printed and electronic formats.

Specific Aim 2. To evaluate the efficacy of the intervention via a randomized, controlled clinical trial of current dual users (Study II). We will compare the intervention developed under Specific Aim 1 with both an assessment-only condition and a generic self-help condition comprising existing smoking cessation booklets. We hypothesize that recipients of our targeted *If You Vape* booklets will show higher rates of tobacco abstinence at 6, 12, 18, and 24 months after enrollment, as compared to both comparison conditions. A secondary hypothesis is that the new intervention will produce higher rates of abstinence from e-cigarettes themselves. To identify mechanism of change, we will also test several *a priori* moderator and mediator variables, including gender, socio-economic status, motivation to quit, nicotine dependence, e-cigarette expectancies, and magnitude of e-cigarette use (frequency, dosage).

Specific Aim 3. To calculate and compare the cost-effectiveness of the interventions. Costeffectiveness data are vital for evaluating the real-world feasibility of an intervention. Small improvements in treatment efficacy may not be justified if they require substantially greater cost. We will compare the interventions not only on outcome efficacy, but on cost-effectiveness with respect to cost per incremental cessation and expected life-years saved.

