C.1.2.3. Cessation. The most relevant study (R01 CA134347) ended data-collection in May, 2014. This study was based on preliminary data suggesting that the *Forever Free* booklets, although developed to prevent relapse, were, in fact, also efficacious for current smokers. This contrasts with the general finding that self-help is minimally effective (1% additional cessation) for smoking cessation (Lancaster & Stead, 2005)..We modified the original *Forever Free* booklets to include instruction on smoking cessation, per se, creating a new version titled, *Forever Free: Stop Smoking For Good*. We randomized 1874 current smokers to three conditions: (1) Usual Care (a standard smoking cessation booklet, *Clearing the Air*, published by NCI); (2) Standard booklets (8 *Stop Smoking For Good* booklets mailed over 12 months); or (3) Enhanced booklets (10 *Stop Smoking For Good* booklets mailed over 18 months, plus 9 brief motivational pamphlets interspersed between booklet mailings). We recently completed preliminary analyses of outcomes through 18 months.

Table 1:	Table 1: Percent Abstinent at 6, 12, and 18 Months in Cessation Study; Significance Levels versus Usual Care														
Analysia		6 Mor	ths Follov	w-Up		12 Mc	onths Follo	w-Up		18 Months Follow-Up					
Analysis	N	UC	SB	EB	N	UC	SB	EB	Ν	UC	SB	EB			
Responde	1064	12.99	15.98	18.37	1046	15.63		29.25	1191	21.13	22.66	33.3			
rs Only	1.304	(ref)	p = .20	p = .02	1246	(ref)	p = .02	p <	1191	(ref)	p = .60	3			
Intent to	1874	9.87	11.40	13.02	1874	10.66		18.81	1874	14.11	14.17	20.4			
Treat			p = .38	p = .08		(ref)	p = .03	p <		(ref)	p = .97	2			
Notes: UC = Usual Care; SB = Standard Booklets; EB = Enhanced Booklets. At 18 Months, difference between EB and SB is significant for Responders Only (p = .001) and Intent to Treat (p =.004) analyses.															
between EE	3 and S	B is si	gnificant f	or Respor	nders C	Dnly (p	= .001) ar	id Intent to	Treat	(p =.00	4) analyse	es.			

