As seen in Table 1, both versions of the intervention were more effective in producing abstinence by 12 months than the comparison Usual Care condition, *but by 18 months, the Enhanced booklets were superior to both Usual Care and Standard booklets.* Although economic analyses have not yet been conducted, these results suggest that the intervention will continue to be far more cost-effective than most other smoking-cessation interventions (e.g., Cromwell et al., 1997; Curry et al., 1998). This study demonstrates that a minimal, but extended, self-help intervention can significantly and cost-effectively improve smoking cessation rates, and it supports our plan to further adapt this intervention for current dual users of tobacco cigarettes and e-cigarettes.

C.1.3. Interventions for Special Populations

Our team has substantial experience creating interventions for special populations of smokers. Using a similar formative strategy as currently proposed, we adapted the *Forever Free* intervention for pregnant women (Quinn et al., 2006). In an RCT (R01 CA94256), we compared these *Forever Free: For Baby and Me* booklets against standard, booklets (Brandon et al., 2012). We found both main effects and moderation by SES. For example, by 12 months postpartum, low-income women were particularly likely to benefit from the intervention (72% vs 51% abstinent at 12 months postpartum, p = .003).

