The primary statistical analyses will assess the effectiveness of the full intervention (eTARGET) in producing smoking cessation compared to the no-treatment control (ASSESS) and the generic smoking cessation booklets(GENERIC). Based on prior published work ([name] et al., 2013), data from our cessation study (C.1.2.3), and considering that the sample will not be limited to treatment-seekers, we estimate no greater than 15% abstinence by 18 months in ASSESS, with at least 5% increments for GENERIC and eTARGET, respectively. We estimated sample size using GEESIZE version 3.1 (Rochon, 2003) with an AR(1) working correlation structure and coefficient of 0.7; adjusted alphas of .017 (ASSESS vs. eTARGET), .025 (ASSESS vs. GENERIC), and .05 (GENERIC vs. eTARGET) following Holm's procedure (Holm, 1979); and abstinence rates that increase from 6 to 18 months, then remain stable through 30 months. Randomizing 2065 participants based on 1:2:2 relative sizes (413 to ASSESS; 826 to GENERIC, and 826 to eTARGET) ensures ≥80% power for all contrasts. We plan to recruit 580, 1160, and 1160 individuals, respectively, in expectation of 17% attrition after baseline assessment, as observed in our prior study.

We initially planned to recruit 500, 1000, and 1000 individuals, respectively, in expectation of 17% attrition after baseline assessment, as observed in our prior study. Based on return rates of the 3-month survey for the first 575 study participants, we now expect 27.5% attrition after baseline. Therefore, we plan to recruit 2900 individuals (400 more than initially planned) with 580, 1160, and 1160 individuals in the ASSESS, GENERIC, and eTARGET conditions, respectively. This will ensure the same sample size for statistical analysis at the higher-than-expected attrition rate.

C.6.3. Data Analysis Overview

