Participants will be randomized into the three conditions using balanced-permuted block randomization with a block size of 10 (2-4-4). Analyses will be conducted with SAS version 9.3 and Mplus Version 7 (Muthén & Muthén, 2008). Frequency distributions and contingency table analyses will be used as a point of departure for more advanced analyses. Multiplicity will be legitimately adjusted as needed for Aim 2, but not for the secondary or exploratory analyses. We will perform attrition analyses, using survival analysis, to test whether the attrition rate differs across intervention arms, if participants and dropouts differ on key variables, and if such variables moderate attrition differences across arms. The median time to attrition and its 95% confidence interval, will be summarized by intervention arm using the Kaplan-Meier method with log-rank test. Any significant variables on those attrition patterns in multivariable Cox Proportional Hazards (PH) models will be accounted for during multiple imputations as well as in the main analysis.

To manage missing data, multiple imputation under the Missing at Random assumption will be applied using a Markov Chain Monte Carlo method (Shafer, 1997) via PROC MI in SAS, given the expected large number of non-monotonic missing data patterns. Preliminary analyses will determine auxiliary variables (e.g., baseline measures that predict smoking status at follow-up) to be used. A post hoc approach (Rubin, 1987) will address the influence of Missing Not at Random (MNAR) on smoking status (i.e., missing is due to smoking). Sensitivity analyses will be performed to assess alternative multiple imputation techniques upon the extent of MNAR influences.

C.6.4. Analytic Plan for Addressing Specific Aims.

C.6.4.1. Specific Aim 1 (see C.2.3.2.) and Aim 3 (see C.5.)

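### Holm covers the three arm pairs, but no contrast over time is named as deciding Aim 2, and the power claim uses a 30-month horizon in a 24-month trial: name the 6–24 month average per pair, keep Holm, and restate power

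*Combined protocol and SAP*

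**What the plan says.** - **Aim.** Specific Aim 2 predicts "higher rates of tobacco abstinence at 6, 12, 18, and 24 months after enrollment" for the targeted booklets (eTARGET) against both comparators.
- **Outcome.** Section C.4.2 calculates point-prevalence abstinence at every assessment and states: "The 7-day criterion will serve as our primary outcome index".
- **Test.** Section C.6.4.2 fits a GEE with condition, time and their interaction. It plans pairwise comparisons of conditions and of time intervals through contrast statements. It names no deciding visit, average or slope.
- **Multiplicity.** C.6.2 gives "adjusted alphas of .017 (ASSESS vs. eTARGET), .025 (ASSESS vs. GENERIC), and .05 (GENERIC vs. eTARGET) following Holm's procedure". C.6.3 adds: "Multiplicity will be legitimately adjusted as needed for Aim 2". Neither gives a rule across visits.
- **Power.** C.6.2 claims at least 80% for all contrasts with 413, 826 and 826 analysed. The inputs are AR(1) correlation 0.7 and "abstinence rates that increase from 6 to 18 months, then remain stable through 30 months". Rates are given at 18 months only: ASSESS no more than 15%, with steps of at least 5 points to GENERIC and then to eTARGET.
- **Follow-up.** C.4.1.3 schedules assessments "at 3-month intervals through 24 months", and C.3.1 (Table 3) and C.4 agree.

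**The concern.** The pairs and the outcome are fixed, but the time dimension is open. With a condition-by-time interaction in the model there is no default overall arm effect, because the condition coefficient depends on how time is coded. The deciding contrast therefore has to be written down. As the text stands, Aim 2 could be claimed from a win at any visit, from wins at every visit, or from one longitudinal contrast. These rules differ widely in error and power.

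The comparison most exposed is GENERIC versus eTARGET, because it carries the case for producing new booklets. The team's previous three-arm trial shows that a conclusion can turn on the visit. Its results table ("Percent Abstinent at 6, 12, and 18 Months in Cessation Study; Significance Levels versus Usual Care") gives Standard booklets versus Usual Care, intent to treat, p = .38, .03 and .97 at 6, 12 and 18 months. The text summarises the 12-month result as "both versions of the intervention were more effective in producing abstinence by 12 months than the comparison Usual Care condition".

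The power statement has a separate defect: its last modelled time point lies six months beyond the last assessment.

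**Working it through.** **1. The plan's own figures.** Holm's steps are .05/3 = .0167 (printed as .017), .05/2 = .025 and .05. The arms sum to 413 + 826 + 826 = 2065. After the expected 27.5% attrition, 2900 × 0.725 = 2102, so 2065 is covered. These reproduce.

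The 80% cannot be reproduced, because the 6- and 12-month rates, the contrast, the link scale, the sidedness and the visit spacing of the 0.7 are not given. It is not a single-visit figure. At 15/20/25% and the printed alphas, two-sided with pooled null variance, power at one visit is 96.1% (ASSESS–eTARGET), 46.0% (ASSESS–GENERIC) and 68.2% (GENERIC–eTARGET). A repeated-measures contrast must have been used.

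**2. Horizon.** Take the equal-weight average over visits.
- Difference D = mean over visits of the arm difference.
- SE² = sum over the two arms of (1/k²) Σᵢ Σⱼ sᵢ sⱼ ρ^|i−j|, with sᵢ² = pᵢ(1−pᵢ)/n.
- Power = Φ(D/SE − z), with z = 2.241 at alpha .025 and 1.960 at .05.

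*Assumed* path: ASSESS 5/10/15/15(/15)%, constant 5-point gaps, ρ = 0.7 per six months. For ASSESS–GENERIC:
- 6–30 months: SE = .01606, D/SE = .05/.01606 = 3.113, Φ(0.872) = 80.8%.
- 6–24 months: SE = .01638, D/SE = 3.053, Φ(0.811) = 79.1%.

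On the logit scale the same path gives 80.2% and then 77.9%.

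Two other *assumed* paths rise in every arm, as C.6.2 requires:
- Late: ASSESS 10.5/11.3/15/15%, gaps at 0.5, 1, 1, 1 of full size.
- Gradual: ASSESS 10/12.5/15/15%, gaps at 1/3, 2/3, 1, 1. For ASSESS–GENERIC, .0400/.01676 = 2.387 gives 55.8%; dropping 30 months, .0375/.01733 = 2.164 gives 46.9%.

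**3. Visit spacing.** Outcomes are collected every 3 months, and C.6.2 does not say to which interval the 0.7 applies. If it is the 3-month correlation, the 6-month value is 0.7² = 0.49.

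Power (%), ASSESS–GENERIC / GENERIC–eTARGET:

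| Assumed path | 6–30, printed alphas | 6–24, printed alphas | 6–24, step-down Holm, 0.7 per 6 months | 6–24, step-down Holm, 0.7 per 3 months |
|---|---|---|---|---|
| Constant gap | 80.8 / 90.8 | 79.1 / 89.1 | 86 / 89 | 94 / 96 |
| Late | 67.1 / 83.1 | 61.1 / 78.2 | 69 / 76 | 82 / 88 |
| Gradual | 55.8 / 74.9 | 46.9 / 66.7 | 53 / 61 | 68 / 76 |

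Step-down Holm lets a pair be tested at a larger alpha once others are rejected, so columns 3 and 4 differ. Dropping 30 months costs 1.7 to 8.9 points. Changing the spacing adds 7 (96 − 89) to 15 (68 − 53) points. ASSESS–eTARGET stays above 94% throughout.

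**4. Error under the possible decision rules.** Simulation with 400,000 runs, normal approximation, 413/826/826, four visits, AR(1) 0.7, two-sided.
- Any visit counts, Holm within each visit, all arms at 15%: some pair declared different, either direction, 12.9% (14.8% at correlation 0.5, 9.4% at 0.9).
- One averaged contrast per pair with Holm: 4.3%.
- GENERIC and eTARGET equal, both above ASSESS: a false finding favouring eTARGET over GENERIC at some visit is 4.1% (15/20/20%) to 6.9% (15/25/25%), against 1.6% to 2.5% for the averaged contrast.
- eTARGET beating both comparators at the same visit, any visit counting: 0.4% when all arms are equal.

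**The case against.** The strongest reply is that the plan already implies one longitudinal test per pair: three alphas for three pairs, a repeated-measures sample-size program and a GEE. C.6.3 also commits to adjusting multiplicity for Aim 2. On that view the 13% belongs to a rule that nobody wrote. It also counts any pair in either direction, whereas Aim 2 predicts eTARGET above both comparators, for which the error is far smaller when all arms are equal. Most of this stands, and it is why the 13% is conditional here. It does not close the gap: the adjustment clause fixes neither a family nor a method, and C.6.4.2 plans time-interval comparisons without saying which is primary.

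The precedent is also limited. It is a preliminary summary of another trial, and the Standard booklets there were mailed for only 12 months, which may explain the fade by 18 months. Here both active arms run a matched 18 months. It illustrates sensitivity to the visit and is not evidence of how this trial will be judged.

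A reader might infer three stronger claims, none supported by the documents:
- *The trial is underpowered.* The inputs needed to check this are missing, and the result turns on the unstated correlation spacing.
- *Holm is misapplied.* It is valid for three named contrasts. The fixed pairing of alphas with pairs is a planning convention.
- *All four visits must be won.* This rests only on the word joining the visits in the aim.

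**Conclusion.** The point holds as a gap in specification together with an inconsistency in the power statement. The contrast that decides Aim 2 is not named, and the power inputs extend six months past the end of follow-up. If any visit could support the claim with no adjustment across visits, family-wise error would be about 13% (9–15% for correlations 0.9–0.5), against about 4% for one averaged contrast per pair. A false preference for eTARGET over an equally effective GENERIC would be about 4–7%.

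The stated 80% is neither confirmed nor refuted. Removing the 30-month visit takes ASSESS–GENERIC from 80.8% to 79.1% on the constant-gap path, and costs more if the gaps open later. Reading 0.7 as the 3-month correlation moves power up by more than that on the paths tried. All power figures rest on assumed 6- and 12-month rates. The documentary findings are firm; the power ranges are illustrations.

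**What to change.** 1. In C.6.4.2, name one primary GEE contrast per arm pair: 7-day abstinence averaged with equal weights over 6, 12, 18 and 24 months. This matches the visits in Aim 2 and the repeated-measures basis of the sample size.
2. State in C.6.3 that Holm is applied to the ordered p-values of these three contrasts, and that all visit-specific contrasts are secondary.
3. Rerun and restate power in C.6.2 with visits ending at 24 months. Give the 6- and 12-month rates per arm, the scale, the sidedness and the interval to which the 0.7 applies.
4. Align the timeline in D.8, which mentions follow-up completion through 18 months, with the 24-month schedule.
5. Fix these choices before outcomes are compared by arm.

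The cost is SAP wording and one power rerun, with no change to data collection. Visit-specific results become secondary, and the restated power may be slightly less favourable. If the arms separate only late, including the 6-month visit in the average gives up some power.
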